9.4 Summary of known and potential risks

This study is considered to be of minimal risk to participants. The main three risks are related to vaccination, sample collection and confidentiality.

The study product vaccine is an already approved and pre-qualified by WHO. There have not been any safety concerns regarding PCV10 and is considered safe (20). In a study assessing lower doses of a pentavalent PCV, doses close to what will be used in this study were not associated with increased frequency of local reactions (27). Administration of fractional doses will result, however, in an increased number of piercings of vial stoppers compared with what they are validated for. Possible stopper failures could include loss of self-sealing capacity, increasing the risk of contamination or leakage, and fragmentation of the stopper material, which could increase the risk of syringe blockage or injection of particles (36). However, a study assessing different vials stoppers found that all stoppers maintained their self-sealing capacity even after 100 punctures (36). Considering this and the presence of a preservative in the vaccine, the risk of multiple piercings is minimal. However, vaccination will be performed following a study specific SOP and vaccinated children will be followed-up to monitor and treat any reactions to the vaccine. A pharmacovigilance officer is permanently in place at the Epicentre Niger research center and with the Sponsor.

If one dose of PCV has an effect in the reduction of VT carriage, serotype replacement could eventually occur. However, the serotypes included in the PCV10 vaccine used in this study are the most common cause of IPD. Consequently, VT carriage is likely to be replaced by non-VT pathogenic serotypes, preventing cases of IPD.

All clinical procedures, including administration of the vaccine and collection of the NP swab, will be performed by adequately trained and experienced personnel under regular supervision to minimize any risk or discomfort to participants.

Data management and confidentiality will all be conducted according to the EU General Data Protection Regulations (GDPR).

9.5 Risk minimization and benefits

The introduction of the swab through a nostril might be particularly uncomfortable to young children. The procedure will be carefully explained to the parent/guardian and if the age of the child allows it will also be explained to the child in an adapted language. The procedure will be carried out by medical study personnel specifically trained to perform this procedure and following a study SOP. Should the COVID-19 pandemic be circulating in the region at the time of the study, a SOP will be in place to ensure proper use of personal protection equipment (PPE), which will be provided, as well as alignment with all public health regulations issued by the Nigerien government and as recommended by international regulators.

At the individual level, children will benefit from immunization with a booster dose of PCV. Increased vaccine coverage will contribute to reduction of pneumococcal associated disease.

At the population-level, the increase in PCV vaccination might have a positive effect on the uptake of other vaccines increase the overall protection against vaccine-preventable diseases. If PCV mass campaigns have an effect in reduction of VT carriage, this will be a benefit for the entire community. The data obtained from this study will be used to inform mass campaigns targeting a large age group in different settings, including emergency situations.

WHO policy regarding handling of multi-dose vaccine vials (WHO/IVB/14.07) will be followed and used to minimize any risk from injections during vaccine campaigns.

Relying on passive surveillance of AEs and SAEs may lead to underreporting, but this will be mitigated by having study staff dedicated to safety follow-up in health centers in the study area.

9.6 Expenses and reimbursements

Participants will not receive any direct financial benefit from participating in the study.

Clinic and treatment costs due to serious adverse events will be covered by the study for all participants during a period of 28 days post-vaccination.

It is not anticipated that participants will travel for any study visits, as they will be home visits. However, if they should occur, reasonable travel expenses for any visits additional to normal care will be reimbursed or a mileage allowance provided as appropriate.

Households participating in the surveys will be offered two bars of soap as a gesture of thanks and to compensate for time taken to participate, a practice that has been commonly accepted in the study area.

9.7 Ethics review and approvals

9.7.1 Declaration of Helsinki

The Investigator will ensure that this study is conducted in accordance with the principles of the Declaration of Helsinki.

9.7.2 ICH Guidelines for Good Clinical Practice

The Investigator will ensure that this trial is conducted in full conformity with relevant regulations and with the ICH Guidelines for Good Clinical Practice (CPMP/ICH/135/95) E6(R2) 2016.

9.7.3 Approvals

The protocol, informed consent form, and participant information sheet will be submitted for ethical review to the MSF Ethical Review Board, the Kenya Medical Research Institute Scientific Ethics Review Unit, and the *Comité National d'Ethique pour la Recherche en Santé* in Niger.

The Investigators will submit and, where necessary, obtain approval from the above parties for all substantial amendments to the original approved documents.

Study authorization will be obtained by the Ministry of Public Health in Niger, and from the drug and pharmacy regulatory authorities "*Autorité Nationale de Réglementation des Médicaments*" in Niger for approval of the importation of the product.

9.8 Study registration

Before study start, the study will be registered on clinicaltrials.gov and PACTR.

9.9 Informed consent

9.9.1 Community consent

The community engagement process will map the willingness and requirements of the community for involvement in the study, to ensure participation and mutual respect of values and actions. A study team will visit the selected villages to discuss community consent with gatekeepers as defined above.

Before study activities, villages will be visited, and information sessions will be held to inform about study activities and assignment of villages to the different study arms. During these sessions, information will be given on the study vaccine, and it will be explained that the vaccination campaign is part of a larger study and that some individuals will be selected to participate in pre and post-vaccination surveys.

Information sessions will be planned to reach the highest number of household's representatives. The involvement of community leaders will be key in assessing the reach of the information sessions. During these sessions the Information notice will be distributed, and parents/caretakers will have the opportunity to ask questions.

9.9.2 Individual consent

During the information sessions, the household representative will be asked to sign an informed consent form if they wish that the children of the target age group living in their household participate in the vaccination activities. On the day of the vaccination activities in a given village, a study team will continue to deliver information about the study and the nature of the vaccination activity, highlighting that participation is voluntary. Children will be asked to come to the vaccination site with a parent or guardian. Households who present to vaccination sites who have not previously signed informed consent documents will be given the opportunity to do so at the vaccination site with dedicated study staff.

Written informed consent will be sought prior to inclusion in the pre- and post-vaccination surveys. The potential participants and their parent(s)/guardian(s) will have the study explained in depth to them and, in addition, will receive a patient information sheet. They will have the opportunity to ask questions to study staff prior to giving consent. Informed, witnessed, written consent will be recorded (ICF) from each participant and applicable parent(s)/guardian(s) for study participation, and other specific aspects of the trial.

The ICFs designed for this study are based on the description in the 2013 Revision of the Helsinki Declaration and other documents related to GCP.

Designated study staff will review the consent form with potential participants or representatives. The consent form will also be verbally explained in the appropriate local language. The informed consent process will ensure with high confidence that potential participants have an understanding of the potential risks and benefit of participation in the study, the study procedures, their right to refuse and/or withdraw from the study at any point without affecting the health services or care they receive, and without having to disclose a reason for their refusal or withdrawal.

9.10 Participant privacy and confidentiality

The study staff will ensure that the participants' privacy is maintained.

No individual information will be collected at vaccination sites.

Pre- and post- survey participants will be identified by initials, age (and date of birth if known), sex and a unique ID number. All documents and electronic data will be stored securely and only accessible by study staff and authorized personnel. The study will make the information anonymous as soon as it is practical to do so.

The Investigator Site File and associated source documents will be retained for at least 10 years after the completion of the study. Written approval from the Sponsor will be obtained prior to destroying records.

All study related documents will be kept in locked cabinets at the study site. Filing cabinets with the study data and the participant information will be locked and accessed only by authorized persons from the Sponsor and Regulatory Authorities.

Participant personal data will be kept confidential and the privacy of all participants will be protected as far as permitted by law and following GDPR regulations. To ensure traceability and following

standard practice, nasopharyngeal samples will be labelled with participant initials, in addition to a unique ID number, sex and age. Only staff involved with the study conduct and local and international regulatory agencies may review these records.

10 Administrative aspects

10.1 Protocol amendments

The Sponsor will amend the study protocol as needed to ensure that the clinical investigations are always conducted according to appropriate and up-to-date protocols. Amendments will be submitted for approval to the regulatory authorities and Ethics Committees. Changes requiring amendments will be defined according to guidance from regulators and include any significant change in the design of the study or the addition of a new test or procedure.

10.2 Protocol deviations and violations

A protocol violation is any departure from the approved protocol, trial documents or any other information relating to the conduct of the study, which may affect the safety of trial participants or the study outcomes. Examples include failure to obtain informed consent (i.e. no documentary evidence) or enrolment of participants that do not meet inclusion/exclusion criteria.

A protocol deviation is any departure from the approved protocol, trial documents or any other information relating to the conduct of the trial that does not result in harm to the trial participants and does not significantly affect the study outcomes. Examples of deviations include missed study visits or a visit date outside the study visit window or an isolated incident of a missed or incomplete study procedure or study evaluation. Serious or repeated protocol violations or deviations will require assessment of the root cause and implementation of corrective and preventive action plans. They may constitute grounds to interrupt the trial.

Any changes from protocol-specified procedures and study-related SOPs occurring during the conduct of the trial will be documented and reported as protocol violations or deviations. Protocol violations will be reported to the Sponsor and reviewing ethical committees, as appropriate and in accordance with the requirements of the involved committees.

10.3 Insurance

ICH GCP defines the extent of the responsibility of the Sponsor.

The involved volunteer participants will be insured, in accordance with applicable laws and regulations, against financial loss resulting from personal injury and/or other damages, which may arise because of this study.

10.4 Funding and other support for the trial

EDCTP will fund the study. The manufacturer will provide vaccines free of charge and other support will be provided by Epicentre in the area of deployment.

11 Data handling and record keeping

11.1 Overview

A Data Management team will be located at the study site. For surveys, all data will be collected on tablet computers using electronic CRFs (eCRF). Information about AE and SAE will be collected at health centers on paper CRFs.

11.2 Investigator site file (ISF)

The investigators will maintain appropriate medical and research records for this study, in compliance with ICH E6 GCP and regulatory and institutional requirements for the protection of confidentiality of participants. The principal investigator, co-investigator, and clinical research staff will have access to records. The investigators will permit authorized representatives of the Sponsor, and regulatory agencies to examine (and when required by applicable law, to copy) clinical records for the purposes of quality assurance reviews, audits and evaluation of the study safety and progress.

The ISF will be maintained at the study site containing at least the following documents and information:

- Signed protocol and amendments
- Electronic questionnaires and paper case report forms (CRF)
- Current informed consent form and all revisions
- Current participant information sheet and all revisions
- Any other written information given to the study team
- Financial aspects of the study
- Insurance statement
- All signed agreements/contracts
- Dated and documented approval of ethics committee and regulatory authorities
- Signed CV's of all investigators and any study personnel (updated regularly as changes occur)
- Instructions for handling of investigational product and study related materials
- Monitoring reports
- Relevant communication
- Signed informed consent forms
- Signed, dated, and completed CRFs
- SAE reporting
- Notification by Sponsor of safety information
- Annual reports to ethics committee and regulatory authorities
- Investigational product accountability
- Authorization/signature sheet
- Documentation of investigational product destruction
- Clinical study report

11.3 Source Documents and CRFs

In this study the following documents have been designated as source documents:

1. Vaccination cards
2. Survey questionnaire responses
3. Hospital records in case of hospitalization
4. Paper versions of AE and SAE CRFs
5. Tally sheets from vaccination sites

If information is collected from different sources other than those specified above, then they will be recorded and documented.

The only paper CRFs will be used to document AEs and SAEs. For the purposes of the surveys, all information will be collected on password-protected tablet computers (see below). A guide for filling in survey questionnaires will be developed and tested with study staff. Data about AE/SAE from paper CRF will be double-entered by data entry clerks using password protected laptops

The study Data Managers are responsible for data management, integrity and security of paper and electronic data. Epicentre Research Department's Data Protection and Compliance Officer supervises those activities. The study's data management plan will describe all activities that will be conducted to ensure the safety and quality of data.

11.4 Record keeping

The ISF including a copy of the final completed CRFs, as well as all source documentation is retained by the investigator and one copy will be maintained by the Sponsor, who will ensure that it is stored with other study documents, such as the signed informed consent forms, protocol, the investigator's brochure and any protocol amendments, in a secure place for 10 years.

11.5 Data management

11.5.1 Hardware and software

The survey questionnaires will be saved directly from tablet computers into a REDCap database. Information about AE/SAE recorded on paper CRFs will be entered directly into REDCap. The REDCap system uses a MySQL database via a secure web interface with data checks used during data entry to ensure data quality. It also includes a complete suite of features to support HIPAA compliance, including a full audit trail and user-based privileges and will conform to ICH GCP requirements. The REDCap system will be activated for the study only after successfully passing a formal design and test procedure. The primary study database will be located on the REDCap server in Paris. Responsibility for implementing the REDCap system lies with the Epicentre. Management and maintenance of the REDCap server lies with the data manager at the study site.

11.5.2 Data security, access, and back-up

The REDCap server will be kept in a locked server-room. Only the system administrators have direct access to the server and back-up tapes. A role concept with personal passwords (site investigator, statistician, monitor, administrator etc.) regulates permission for each user to use the system and database, as he/she requires.

All data are transferred to the database using Secure Sockets Layer (SSL) encryption. Each data point has attributes attached to it identifying the user who entered it with the exact time and date.

Retrospective alterations of data in the database are recorded in an audit table. Time, table, data field and altered value, and the person are recorded (audit trail).

A multi-level back-up system is implemented. Back-ups of the whole system including the database are run internally several times per day and on external tapes once a day. The back-up tapes are stored in a secure location.

11.5.3 Archiving

The Sponsor will securely store the final study database for at least 10 years. The Sponsor will also keep the Trial Master File and interim and final reports both in electronic and in hard copy form for at least 10 years.

12 Data Analysis

Analysis of all endpoints will be described in a Statistical Analysis Plan. This SAP will include all conventions on data, descriptive and statistical analyses to be performed on collected data during the conduct of the study. A brief overview is provided below.

Information on the total number of individuals per cluster for each of the following categories will be presented: screened individuals, screen failures (together with reasons for screen failure), consented participants for the baseline survey, the vaccination and the follow up survey.

Participant demographics and baseline characteristics will be described at the cluster level. For each arm of the trial the number of clusters, the average number of clusters by demographic and baseline characteristics, such as household composition, average prevalence of exposure to indoor smoke, etc will be described and compared to ensure comparability.

All analyses of outcome will be performed at the cluster level, controlling for clustering effects. For each cluster we will calculate the prevalence of NP carriage and present VT carriage in clusters allocated to full dose, fractional dose and control arm, including the 95% confidence interval.

Proportions will be compared using chi square or Fisher's exact test, as appropriate and adjusting for the clustering effect accounting for the intracluster correlation coefficient.

For the analysis of superiority of the full dose vaccination arm compared to the control arm, the comparisons will be done using a chi square test at the 0.05 significance level.

For the non- inferiority analysis, the 95%CI around the difference in the proportion of children with VT carriage (full dose group – fractional dose group) will be calculated and the non-inferiority will be achieved if the lower limit of this 95%CI is >-7.5%.

All sensitivity analyses and adjusted analyses will be described in the SAP. Sensitivity analyses will include, but not be limited to, analyses investigating potential seasonal differences in NP carriage of pneumococci.

Safety analysis will be based on the entire study population. Safety and tolerability of PCV10 will be assessed by comparing the frequency (%) of AEs and SAEs in full-dose and fractional-dose arms to the control arm using the Fisher's exact test. Safety data will be presented in tabular and/or graphical

format and summarized descriptively. Data will be analyzed according to an intention-to-treat approach. In the unlikely event of clusters receiving incorrect interventions, or being only partially vaccinated, per-protocol analyses will be repeated on the primary endpoint.

13 Quality assurance and control

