7.1 Overall study design

A Phase IV, 3-arm, observer-blinded, cluster-randomized controlled trial will be implemented in rural villages of the Madarounfa District of Niger. A schematic representation of the trial is presented in

After results of the baseline survey are known, clusters will be randomized to full dose, fractional dose or control arm in 3:3:1 allocation ratio. The trial will be conducted in 63 clusters, with 27 randomized to full dose arm, 27 randomized to fractional dose arm and 9 randomized to a control arm. Clusters will be composed of a village or group of closely-neighbouring villages that share a school or market, and will be limited to a population of between 500 and 4000 persons. Stratified randomization will be used to account for proximity to the nearest health centre (<5 km vs \geq 5 km). In the event of significant imbalance in carriage of VT pneumococci between clusters in the baseline survey, randomization will also be stratified by baseline prevalence. Vaccination will target all children aged 1 to 9 years of age residing in the selected villages. (If baseline survey data unexpectedly shows very low prevalence of carriage at the extremes of this age range, the target age group may be adjusted upon recommendation of the trial steering committee.) We estimate that children eligible for the vaccination campaigns will represent 30% of the total population. With an estimated average of 2000 people per cluster, vaccination will target 600 children 1-9 years of age in each cluster receiving vaccine. In total, in the 54 clusters receiving vaccine, the mass vaccination campaign with single full- or fractional-dose PCV will target approximately 32,400 children 1-9 years of age.

[figure not shown]
Prior to the mass vaccination campaign, a cross-sectional survey will be implemented to estimate community-level carriage of VT pneumococci, as well as to collect data on household composition, social interactions and PCV vaccination coverage in the routine EPI. A total of 36 households in each cluster will be invited to participate in the cross-sectional survey. This sample size may be re-evaluated based on the results of the baseline survey.

Selection of households will be based on probability sampling. The required number of households in each cluster will be randomly selected using simple random sampling based on an exhaustive list of heads of household in the cluster. Six months after the mass vaccination campaign, the post-

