7.2.1 Summary of vaccine safety

The most frequently reported adverse reactions include fever, irritability, injection site reactions including pain, erythema, swelling or induration, decreased appetite, drowsiness and diarrhoea. Serious reactions are rare.

Extending the use of the 5-dose multi-dose vial to provide 25 administrations may increase the risk of injection site reactions e.g. swelling and localised inflammation due to contamination. The preservative contained in the vial should minimise this risk.

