7.11 Randomization and blinding procedures

Following the results of the baseline survey, clusters will be randomized in a 3:3:1 ratio, with 27 clusters randomized to receive a campaign with the full dose, 27 clusters randomized to receive a campaign with the fractional dose and 9 clusters randomized to the control arm. Randomization will be stratified by proximity to nearest health center (<5 km vs. ≥5km). In the event of significant imbalance in carriage of VT pneumococci between clusters in the baseline survey, randomization will also be stratified by baseline prevalence. An equal or proportional number of clusters will be randomized to each study arm from each stratum.

The randomization list will be generated by an independent statistician with no other contact with trial participants.

Study implementation will be blinded to the extent possible. Vaccination nurses will not be blinded to the vaccine they are giving, but they will not communicate vaccine allocation to other members of the team or to participating villages. Villages randomized to the control arm will not receive any “dummy” intervention, so will not be blinded to their group allocation. The trial will be observer-blind in that personnel at KWTRP will be blinded to group allocation until after the completion of culture and serotyping in each survey.

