4.3 Statistical Analysis

All results will be displayed by intervention group (full dose, fractional dose or control).

Descriptions of the study population will be provided at the individual level and at the cluster level as appropriate. Statistical analyses to demonstrate superiority and non-inferiority will be performed at the individual level. Non inferiority will be tested if the superiority of the full dose is shown; therefore, no adjustment for multiplicity is necessary.

Comparison between groups will be done at the cluster level using Student's t-test for continuous variables and Chi square test (or Fisher's exact test if more appropriate) for categorical variable.

Safety analysis will be done at the individual level only, and comparison for categorical variables will be done using a Chi square test (or Fisher's exact test if more appropriate). All comparisons will be done at the 0.05 significance level.

Prevalence of carriage will be presented with a 2 sided 95% confidence interval.

All statistical analysis will be performed on the statistical software Stata version 17 or later.

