4.3.3 Safety Analysis

Safety analysis will be based on the entire study population.

Any adverse events occurring within 7 days after vaccination, serious adverse events, or deaths will be summarized as n (%) of participants having experienced the AE(s), and SAEs or death by arms. Comparisons will be done between full-dose and fractional-dose arms with the control arm, using a Fisher's exact test.

All AEs will be coded to a "Preferred Term" (PT) and primary associated "System-Organ Class" (SOC) according to the MedDRA dictionary (Medical Dictionary for Regulatory Activities, version 25.0).

Counts and proportions will be provided overall and for each PT within each SOC. AE(s) will be tabulated overall and by grade, and by type of AEs:

- AEs non SAEs occurring with 7 days after vaccination
- SAEs
- SAEs leading to death

5. Statistical Tables to be Generated

<Consider appropriate tables for each of these categories and some examples are provided>

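### Between-arm inference on SAEs and deaths is a significance test against the nine-cluster control arm with no effect estimate or confidence interval, so it does not show what excess risk the data exclude

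*Combined protocol and SAP*

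**What the plan says.** Protocol section 12 (Data Analysis) sets the safety analysis: "Safety and tolerability of PCV10 will be assessed by comparing the frequency (%) of AEs and SAEs in full-dose and fractional-dose arms to the" control arm, by Fisher's exact test. SAP 4.3.3 has the same plan: numbers and percentages of children with AEs, SAEs or death by arm, then "Comparisons will be done between full-dose and fractional-dose arms with the control arm, using a Fisher's exact test". SAP 4.3 places the safety analysis at the individual level only, where "comparison for categorical variables will be done using a Chi square test (or Fisher's exact test if more appropriate"), and adds that "All comparisons will be done at the 0.05 significance level".

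Neither document names a risk difference, risk ratio, confidence interval or detectable excess for SAEs or deaths. Carriage is treated differently. SAP 4.3 says "Prevalence of carriage will be presented with a 2 sided 95% confidence interval", and SAP 4.3.2 adds GEE risk differences with 95% CIs and a margin of 7.5 percentage points for non-inferiority. The safety comparisons listed are each vaccine arm against control; fractional against full dose is not among them.

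The test is not the whole safety assessment. Section 12 also promises a descriptive summary. SAP 4.3.3 and the SAP table and listing shells add tabulation by MedDRA term, severity, relatedness and outcome, and death narratives. Protocol 8.1 requires a causality assessment of every SAE. Protocol 8.5 and 13.3 provide DSMB reporting and three-monthly DSMB meetings.

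**The concern.** The third secondary objective is to assess AEs and SAEs after fractional and full doses, and the trial is meant to inform policy on mass campaigns. A reader of that result needs to know how large an increase in SAEs or deaths the data still allow. A p-value with two percentages does not say. It can exceed 0.05 because the risks are alike, or because there are too few events to tell.

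The second explanation is a live one here. The comparator is the smallest arm ("27 clusters randomized to receive a campaign with the fractional dose and 9 clusters randomized to the control arm"), and if SAEs are uncommon it will contain only a handful of events. The plan uses interval-based inference for carriage but leaves it out for safety, where the counts are likely to be sparser. As written, the plan does not guard against a non-significant comparison being taken as reassurance.

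**Working it through.** **Inputs from the documents.** There are 27 clusters in each vaccine arm and 9 in control (protocol 7.11). On cluster size, "vaccination will target 600 children 1-9 years of age in each cluster receiving vaccine" (protocol 7.1). The level is 0.05 (SAP 4.3); sidedness is not stated for safety, so two-sided is assumed.

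**Reproducing the plan's figure.** 54 × 600 = 32,400 children targeted, as protocol 7.1 states. The same rule gives 27 × 600 = 16,200 per vaccine arm and 9 × 600 = 5,400 in control. The 5,400 is derived from planning averages; the documents do not state it. They also state no power for safety.

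**Assumed input.** The documents give no SAE risk, so a range of control risks p is used. A true doubling means 2p in the vaccine arm.

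**Method.** Let X0 ~ Binomial(5,400, p) and X1 ~ Binomial(16,200, 2p). Power is the sum of P(X0 = x0) × P(X1 = x1) over all pairs where the two-sided Fisher p-value is at most 0.05 and the vaccine arm has the higher risk. The miss rate is 1 − power. Children are treated as independent.

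| Control risk | Expected events, control v vaccine | Power | Miss rate |
|---|---|---|---|
| 0.02% | 1.1 v 6.5 | 0.011 | 99% |
| 0.05% | 2.7 v 16.2 | 0.120 | 88% |
| 0.1% | 5.4 v 32.4 | 0.281 | 72% |
| 0.2% | 10.8 v 64.8 | 0.598 | 40% |
| 0.3% | 16.2 v 97.2 | 0.791 | 21% |
| 0.5% | 27.0 v 162.0 | 0.956 | 4% |

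For a 1.5-fold rise the miss rates are 91%, 80% and 52% at 0.1%, 0.2% and 0.5%. Larger effects are detected better: at 0.1%, power is 78% for a tripling and 97% for a fourfold risk.

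**Sensitivity at 0.1%, doubling.** The vaccine-arm denominator is children actually vaccinated (SAP 3.1.5). At 70% to 90% coverage (11,340 to 14,580 children) the miss rate stays at about 72%. Pooling both vaccine arms (32,400) raises power only from 28% to 31%, so the control arm is the limit. Positive within-cluster correlation would reduce the information further. The only intracluster correlation in the documents, 0.02, is for carriage, so no figure is attached to this for SAEs.

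**What the planned output would hide.** Two illustrative results, with exact conditional limits for the risk ratio:

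- 41/16,200 v 6/5,400: Fisher p = 0.062, not significant. The ratio is (41/16,200)/(6/5,400) = 2.3, with 95% CI 0.96 to 6.6.
- 18/16,200 v 6/5,400: identical observed risks of 1.11 per 1,000. The ratio is 1.0, with 95% CI 0.38 to 3.1. The difference is 0 ± 1.96 × √[0.00111 × 0.99889 × (1/16,200 + 1/5,400)], or ± 1.03 per 1,000.

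Both would appear in the planned table as non-significant. The first is compatible with a more than sixfold risk. The second still allows a threefold risk, or about one extra SAE per 1,000 children.

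**The case against.** The strongest reply is that this overstates the role of the test. Three readings that a reader might draw from the plan are not supported by it.

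- *That Fisher's test is the whole safety assessment.* It is not, given the descriptive tables, causality assessment, narratives and DSMB review, and SAP 4.3 also allows a chi square. But those elements judge individual cases or list counts. None estimates the difference between arms.
- *That a non-significant result will be declared safe.* No section says so. There is no safety hypothesis or decision rule, and the objective is worded as assessing occurrence. What stands is narrower: the plan names the test as the way safety is assessed and reports nothing that would show its imprecision.
- *That the test has a known 72% miss rate.* That figure belongs to one assumed control risk. Protocol 7.2.1 says "Serious reactions are rare", but that describes vaccine reactions. The outcome compared is any SAE, including hospitalisation or death from any cause, so the sentence does not fix the background risk. At about 0.5% the test detects a doubling well.

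It is also fair that counts and denominators are to be tabulated, so a reader could compute a crude interval. That interval would ignore clustering and would not be prespecified. The reply narrows the claim but does not remove the case for reporting estimates.

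**Conclusion.** The point holds in this form: the only planned between-arm inference on SAEs and deaths is an individual-level significance test of each vaccine arm against control, without an effect estimate or interval. For a true doubling its miss rate runs from 99% to 4% over assumed control risks of 0.02% to 0.5%, and is at least 40% at 0.2% or below. These figures rest on 600 children per cluster, full coverage, a two-sided test and independent children. The documents supply no SAE risk with which to choose within the range.

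This is a weakness in how the safety result will be expressed. It does not show that the campaigns are unsafe or that the investigators intend to claim safety from a p-value, and it leaves the carriage analysis untouched. It is worth correcting because the data needed are already to be collected.

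**What to change.** In SAP 4.3.3 and protocol section 12, make estimation the planned inference for SAEs and for deaths:

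- Report the risk difference per 1,000 children and the risk ratio, with two-sided 95% CIs that allow for clustering, for full dose v control and fractional dose v control. Add fractional v full.
- When counts are very sparse, use exact conditional limits and note that these ignore clustering. Fix the event count for the switch in advance, because methods can disagree: for 41 v 6 events, a simple Wald interval for the difference, 1.42 ± 1.96 × 1,000 × √[0.00253 × 0.99747/16,200 + 0.00111 × 0.99889/5,400], runs from 0.24 to 2.60 per 1,000, although Fisher gives p = 0.062.
- Report the upper limit as the excess risk that the data do not exclude. No preset margin is needed.
- State that p > 0.05 is not evidence of no difference, and keep any Fisher p-value as descriptive only.

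The cost is wording in two places and a few table columns, with no extra data or participants. The downside is a more cautious safety statement, because the intervals will be wide.
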